8.6.5. Cardiac Telemetry Monitoring

All cardiac telemetry data will be listed.

Where data available, shifts from baseline tables will be provided for cardiac telemetry monitoring data.

8.6.6. Other Assessments

Medical history will be listed.

All other safety and tolerability assessments not detailed in the above sections such as physical examination and cardiac telemetry monitoring will be listed only.

8.6.7. Safety and Tolerability Statistical Methodology

No inferential statistical analysis is planned.

9. INTERIM ANALYSES

No interim analysis is planned.

10. SIGNIFICANT CHANGES FROM THE PROTOCOL-SPECIFIED ANALYSES

There were no significant changes from the protocol -specified analyses.

This statistical analysis plan (SAP) was developed after review of protocol CBP-307AU002 (Version 5.0 dated 12 January 2022) for the study “A Phase I, Multicenter, Randomized, Double-blind, Double-dummy, Placebo- and Positive-Controlled Study to Investigate the Effects of CBP-307 on the QTc Interval in Healthy Subjects” and the ERT contract/proposal. This document defines the populations to be analyzed and provides full details of the statistical analyses, data displays, and algorithms to be used for data derivations to aid in the production of the statistical output and the statistical section of the cardiac safety report in regard to electrocardiogram (ECG) and concentration-QTc analyses. Relevant subject characteristics as well as the electrocardiographic parameters that will be evaluated are described along with the specific statistical methods.

3 Study Design

This will be a Phase I, randomized, double-blind, double-dummy, placebo-controlled, positive-controlled, multi-site, 3-arm study to investigate the effects of therapeutic and supratherapeutic oral doses of CBP-307 on the QTc interval in healthy male and female subjects.

In this study, approximately 68 healthy subjects (at least 30% for each sex) will be randomized into 2 groups (Group 1 and 2) with 34 subjects in each. Group 2 consists of 2 sub-groups (Group 2A and 2B) and each sub-group will be randomized with 17 subjects. Randomized subjects will receive the assigned study drug as a single dose in the morning under fasting conditions on Days 1, 2, 3 to 6, 7, to 15, and on Day 16 (placebo will be administered to all subjects on Day -1).

The following treatments will be administered:

- Starting doses of CBP-307 for titration (0.05 mg on Day 1 followed by an up-titrated dose of 0.1 mg on Day 2)
- A therapeutic dose of CBP-307 (0.2 mg, Days 3 to 6)
- A supratherapeutic dose of CBP-307 (0.5 mg, Days 7 to 15)
- Placebo (matched to moxifloxacin and CBP-307)
- Moxifloxacin (400 mg)

Moxifloxacin will be used as a positive control to determine the assay sensitivity of this study with an expected peak QT effect (placebo-corrected change-from-baseline QTcF; $\Delta\Delta\text{QTcF}$) of 10 to 15 ms.

Potential subjects will be screened to assess their eligibility to enter the study within 27 days prior to the first dose administration. Subjects will be admitted into the study site on Day -2 (or on Day -4 depending on the clinical site’s requirement for Coronavirus Disease 2019 [COVID-19] testing) and will remain at the study site until discharge on Day 19.

4 Cardiodynamic ECG Assessment

4.1 ECG and Pharmacokinetic Sample Collection

Continuous Holter ECG recordings will be performed before dosing for 25 hours on Days -1, 1, 6, 15, and 16 and continue through 12 or 24 hours post-dose. Replicate 12-lead ECGs will be extracted from the continuous recording prior to dosing (-30 minutes) and 0.5, 1, 2, 3, 4, 6, 8, 12, and 24 hours post-dose on each day. At each time point, up to 10 ECG replicates will be extracted from a 5-minute time window (the last 5 minutes of the 15-minute period when the subject is maintained in a supine, quiet position). The ECG effects of CBP-307 will be tested on data from Day -1 (baseline for both groups), Day 6 (therapeutic concentrations versus placebo), and Day 15 (supratherapeutic concentrations versus placebo). Assay sensitivity with moxifloxacin will be evaluated using ECG data collected on Days -1, 1, 15, and 16.

Pharmacokinetic blood samples will be collected at the following time points: prior to dosing and 0.5, 1, 2, 3, 4, 6, 8, 12, and 24 hours after dosing on each PK sampling day (Days 1, 6, 15, and 16; sample collection windows are as follows: ± 2 minutes for 0.5 hours post-dose, ± 5 minutes for 1 to 4 hours post-dose, ± 10 minutes for 6 to 8 hours post-dose, and ± 30 minutes for 12 to 24 hours post-dose). Additional PK samples will be collected at 72 and 96 hours following dosing on Day 15 (sample collection window: ± 30 minutes).

All Holter/ECG data will be collected using M12R continuous 12-lead digital recorders and the M12A Enterprise Holter System Client (Global Instrumentation, LLC, Manlius, NY, USA). The equipment will be supplied and supported by ERT.

ECG intervals will be measured by the core laboratory in a blinded manner using the Early Precision QT technique (EPQT) (see [Appendix A](#) for more details). The ECG database will be locked before any statistical analysis is undertaken.

4.2 Cardiodynamic ECG Objectives

For the purpose of this analysis plan, objectives related to ECG assessment are described.

The primary ECG objective of the study is to evaluate the effect of therapeutic and supratherapeutic CBP-307 plasma concentrations on the heart-rate corrected QT interval (QTc) in healthy subjects.

The secondary ECG objectives of the study are:

- To demonstrate assay sensitivity of the study to detect a small QT effect using moxifloxacin as a positive control.
- To evaluate the effects of therapeutic and supratherapeutic multiple oral doses of CBP-307 on HR, PR and QRS intervals, and T-wave morphology.

4.3 Cardiodynamic ECG Endpoints

The primary ECG endpoint of this study is the change-from-baseline QTcF (Δ QTcF).

The secondary endpoints are:

- Change-from-baseline HR and PR and QRS intervals (Δ HR, Δ PR, and Δ QRS);
- Placebo-corrected change-from-baseline HR, QTcF, PR, and QRS ($\Delta\Delta$ HR, $\Delta\Delta$ QTcF, $\Delta\Delta$ PR, and $\Delta\Delta$ QRS);
- Categorical outliers for QTcF, HR, PR, and QRS;
- Frequency of treatment-emergent changes for T-wave morphology and U-wave presence

5 Statistical Methods

5.1 General Methodology

All statistical analyses will be performed using the statistical software SAS for Windows Version 9.4 or higher (SAS Institute, Inc., Cary, NC). Data collected from all subjects enrolled in the study who receive at least 1 dose of study treatment (CBP-307, moxifloxacin, or placebo) will be presented in data listings. Both observed values and change-from-baseline values for each subject will be given where applicable. All continuous data will be listed with the same precision as will be presented in the database. Data listings will be sorted by subject ID, treatment, visit (or day), and time point. Missing values will be represented by an empty cell and no imputation will be made.

For all descriptive statistics of continuous ECG parameters (i.e., HR, PR, QRS, and QTc), data will be summarized including number of subjects (n), mean, median, standard deviation (SD), 90% confidence interval (CI), minimum, and maximum by treatment and time point. For all modeling results of the by-time-point analysis of change-from-baseline values of continuous ECG parameters, n, least squares (LS) mean, standard error (SE), and 90% CI will be included. Modeling results of the by-time point analysis of placebo-corrected change-from-baseline will also include LS mean, SE, and 90% CI. Mean and median values will be rounded to the nearest tenth. SD, SE, and CI will be rounded to the nearest hundredth. For the concentration-QTc analysis, 2 decimal places will be shown for all effect estimates for all results which have an absolute value greater than 0.05. Each effect estimate with an absolute value ≤ 0.05 will be displayed with 2 significant figures. The CI of the effect estimate will display 1 more decimal place than the effect estimate. SE and *P* values will be reported with 4 digits and *P* values < 0.0001 will be reported as < 0.0001 . Degrees of freedom (*df*) and *t*-value will be reported to the nearest tenth and nearest hundredth, respectively. Percentages will be rounded to the nearest tenths decimal place.

5.2 Analysis Populations (Subject-Level) and Record-Level Analysis Sets

The analysis populations (subject-level) for cardiodynamic ECG assessment are defined as follows ([Table 1](#)).

Table 1 Analysis populations (subject-level) for cardiodynamic ECG assessment

Analysis Population	Definition
PK population	All subjects who received at least 1 dose of study treatment (therapeutic and supratherapeutic doses of CBP-307, moxifloxacin) and have evaluable PK data of any of the analytes (CBP-307 and moxifloxacin). A subject will be excluded from the PK summary statistics and statistical analysis if the subject has an adverse event of vomiting that occurs at or before 2 times median time to maximum concentration.
QT/QTc population	All subjects who received at least 1 dose of study treatment (therapeutic and supratherapeutic doses of CBP-307, moxifloxacin, or placebo) with measurements at baseline as well as on-treatment with at least 1 post-dose time point with a valid Δ QTcF value. The QT/QTc set will be used for the by-time point, categorical, and morphological analyses of cardiodynamic ECG parameters.
PK/QTc population	All subjects who are in both the PK and QT/QTc populations with at least 1 pair of post-dose PK and Δ QTcF data from the same time point as well as subjects in the QT/QTc population who received placebo. The PK/QTc Set will be used for the concentration-QTc (C-QTc) analysis and assay sensitivity. PK/QTc Set will be defined for CBP-307 and for moxifloxacin.

Table 2 defines the observations that will be included at a record/time point level in the statistical analyses described in this SAP.

Table 2 Record-level analysis sets for cardiodynamic ECG assessment

Analysis set	Definition
By-time point analysis set	Each post-baseline time point that has a nonmissing change-from-baseline observation. Defined for all continuous ECG parameters for subjects in the QT/QTc population.
Categorical analysis set	For continuous ECG parameters, each post-baseline time point that has a nonmissing change-from-baseline observation. For all categorical ECG parameters, each evaluable post-baseline time point that has an evaluable record at baseline, i.e., treatment-emergent changes can be assessed. Defined for all subjects in the QT/QTc population.
Concentration-QTc analysis set	All time points in the by-time point population that have a corresponding planned PK collection at the same time point as well as time points in the by-time point analysis with subjects receiving placebo. Time points at which no PK data are available for nonplacebo subjects will not be retained. Defined for QTc for subjects in the PK/QTc population.

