5.3 Baseline

Baseline for the assessment of the ECG effect of CBP-307 (CBP-307 in Group 1 versus placebo in Groups 2A and 2B) will be time-matched values on Day -1 ([Table 3](#)).

For assay sensitivity in Groups 2A and 2B, the following baselines will be used:

- Group 2A: For moxifloxacin administered on Day 1 (defined as Period 1 Day 1), baseline will be Day 16 (defined as Period 1 Day -1), on which subjects are administered placebo. For placebo-correction in this group, placebo values will be derived from Day 15 (defined as Period 2 Day 1) on which subjects are administered placebo, and baseline will be obtained on Day -1 (defined as Period 2 Day -1).
- Group 2B: For moxifloxacin administered on Day 16 (defined as Period 2 Day 1), baseline will be Day 1 (defined as Period 2 Day -1), on which subjects are administered placebo. For the placebo-correction in this group, Day -1 (defined as Period 1 Day 1) values will be used as placebo (no treatment) and baseline will be obtained on Day 15 (defined as Period 1 Day -1).

For T-wave morphology and U-wave presence, baseline includes findings observed in any replicates from all time points that constitute baseline.

Table 3 Treatment administration and baseline definition

Day	Treatment Arm Group 1	Control Arm	
		Group 2A	Group 2B
-1	CBP-307 placebo Baseline for T1, T2, T3	CBP-307 placebo Baseline for T5 and T6; Baseline for T8 moxifloxacin- placebo on Day 15	CBP-307 placebo Baseline for T4, T5 and T6; T8: moxifloxacin-placebo on Day -1;
1	CBP-307 0.05 mg Moxifloxacin-placebo T1: CBP-307 0.05 mg on Day 1	400 mg Moxifloxacin CBP-placebo T7: moxifloxacin on Day 1	Moxifloxacin-placebo CBP-placebo T4: corresponding placebo on Day 1; Baseline for T7 on Day 16
6	CBP-307 0.2 mg T2: CBP-307 0.2 mg on Day 6	CBP-307-placebo T5: corresponding placebo on Day 6	CBP-307-placebo T5: corresponding placebo on Day 6
15	CBP-307 0.5 mg T3: CBP-307 0.5 mg on Day 15	CBP-307-placebo T6: corresponding placebo on Day 15 T8: moxifloxacin-placebo on Day 15	CBP-307-placebo T6: corresponding placebo on Day 15; Baseline for T8 moxifloxacin- placebo on Day -1
16	CBP-307 placebo Moxifloxacin-placebo (not analyzed)	CBP-307 placebo Moxifloxacin-placebo Baseline for T7 on Day 1	CBP-307 placebo 400 mg Moxifloxacin T7: moxifloxacin on Day 16

Note: To facilitate analysis, the nested crossover design for the moxifloxacin/placebo comparison for assay sensitivity needs to be coded following a 2-period crossover study design

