6.1 Concentration- QTc Analysis (Primary Analysis)

The relationship between CBP-307 plasma concentrations and change-from-baseline $QTcF$ ($\Delta QTcF$) will be quantified using a linear mixed-effects modeling approach with $\Delta QTcF$ as the dependent variable, time-matched concentrations of CBP-307 as the exploratory variate (0 for placebo), treatment (active=1 or placebo=0), and time (i.e., post-baseline time points on Days 1, 6, and 15: categorical) as fixed effects, and a random intercept and slope for concentrations per subject (Garnett et al¹). Centered baseline $QTcF$ (i.e., baseline $QTcF$ for individual subject minus the population mean baseline $QTcF$ for all subjects) will be included in this model as an additional covariate. If necessary, a sensitivity analysis will be performed using the model without this term. CBP-307 plasma concentrations below the quantifiable limit at pre-dose will be set to zero and after dosing will be set to 1/2 the lower limit of quantitation in the concentration- QTc analysis.

An unstructured covariance matrix will be specified for the random effects. If convergence cannot be achieved even after appropriate rescaling of the concentrations, the random effect on the slope and intercept will be dropped, in this order, until convergence is achieved. The degrees of freedom of estimates will be determined by the Kenward-Roger method. From the model, the slope (i.e., the regression parameter for concentration) and the treatment effect-specific intercept

(defined as the difference between CBP-307 and placebo) will be estimated together with the 2-sided 90% CI. The estimates for the time effect will be reported with degrees of freedom and SE.

For the assessment of the ECG effect of CBP-307 versus placebo, the time term incorporated into the models (both by-time point analysis and concentration-QTc analysis [or assay sensitivity]) includes the single pre-dose time point and all post-dose time points on Days 1, 6, and 15, and Days 1 and 16 for active versus placebo and moxifloxacin versus placebo, respectively. All times are relative to the time of dosing on that day which is considered the first dose for the assay sensitivity analysis. For the analysis of CBP-307 versus placebo, the first dose of study treatment is on Day 1.

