6.4 Categorical Analysis

Results for categorical outliers will be summarized in frequency tables with counts and percentages for both number of subjects and number of time points. Subject data will be summarized using the count of distinct subjects that fall into the category and the percentage of the total number of subjects. Time point data will be summarized using the count of time points at which the assessments fall into the category and the percentage of the total number of time

points at which assessments are performed. Counts (either number of subjects or number of time points) for each treatment group will be used as the denominator in the calculation of percentages unless otherwise specified.

A subject or time point will be determined as an outlier if the following criteria (which are assessed separately) are met for the ECG intervals ([Table 5](#)).

Table 5 Criteria for determining a subject or time point outlier

ECG interval	Categorical outlier criteria
QTcF	Treatment-emergent value of > 450 and ≤ 480 ms when not present at baseline (new onset)
	Treatment-emergent value of > 480 and ≤ 500 ms when not present at baseline (new onset)
	Treatment-emergent value of > 500 ms when not present at baseline (new onset)
	Increase of QTc from baseline of > 30 and ≤ 60 ms
	Increase of QTc from baseline > 60 ms
PR	Increase of PR from baseline $> 25\%$ resulting in PR > 200 ms
QRS	Increase of QRS from baseline $> 25\%$ resulting in QRS > 120 ms
HR	Decrease of HR from baseline $> 25\%$ resulting in HR < 50 bpm
	Increase of HR from baseline $> 25\%$ resulting in HR > 100 bpm

All outliers will be summarized for each treatment on the basis of incidence rates. A subject will be counted only once for a particular outlier event if the subject experiences more than 1 episode of that event. The total number of time points will be based on the number of observed time points across all subjects within a treatment group.

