6.5 Morphological analysis for T-wave and U-wave

Morphological analyses will be performed with a focus on detecting changes in T-wave morphology and appearance of abnormal U-waves. The analyses will evaluate change-from-baseline (i.e., treatment-emergent changes). For each category of T-wave morphology and of U waves, the category will be deemed as present if observed in any replicates at the time point. For baseline, the category will be deemed as present if observed in any replicates from all time points that constitute baseline.

The analysis results for T-wave morphology and U-wave presence will be summarized in frequency tables with counts and percentages for both number of subjects and number of time points. The number and percentage of subjects in each treatment group having changes from baseline that represent the appearance of the morphological abnormality will be also summarized. The total number of time points having a particular change event will be summarized in terms of number and percentage based on the number of observed time points across all subjects within a treatment group.

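### The categorical and T-/U-wave rules do not exclude the pre-dose ECG on Day 1 and on the moxifloxacin day, so a recording made before the active drug can be tabulated as treatment-emergent

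*SAP*

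**What the plan says.** All references are to the cardiodynamic SAP.

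- **Record rule (Section 5.2, Table 2).** The categorical set takes "For continuous ECG parameters, each post-baseline time point that has a nonmissing change-from-baseline observation". For morphology it takes "each evaluable post-baseline time point that has an evaluable record at baseline, i.e., treatment-emergent changes can be assessed". The by-time point set in the same table has the same condition as the first of these.
- **Time term (Section 6.1).** The factor is described as post-baseline time points, and the section then states that it "includes the single pre-dose time point and all post-dose time points on Days 1, 6, and 15". The same sentence covers the moxifloxacin comparison.
- **ECG schedule (Section 4.1).** ECGs are extracted "prior to dosing (-30 minutes) and 0.5, 1, 2, 3, 4, 6, 8, 12, and 24 hours post-dose on each day".
- **Baseline (Section 5.3).** For CBP-307 it "will be time-matched values on Day -1". For moxifloxacin in Group 2A, "baseline will be Day 16 (defined as Period 1 Day -1), on which subjects are administered placebo". In Group 2B, Day 1 serves as baseline for Day 16.
- **Outlier definition (Section 6.4, Table 5).** A QTcF value is treatment-emergent if the category was absent at baseline. Section 6.5 uses the same logic for T and U waves, with baseline covering every replicate at every baseline time point.
- **Denominator (Section 6.4).** "The total number of time points will be based on the number of observed time points across all subjects within a treatment group".
- **Table list (Section 8.1).** Tables 14.1.9.1 and 14.1.9.2 (HR, PR, QRS) require the value to be post-dose. Tables 14.1.7, 14.1.8 and 14.1.10 (QTcF, T and U waves) carry no such condition.

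**The concern.** Because baseline is a different day, the -30 minute ECG on a dosing day has its own change from baseline and passes the Table 2 condition. On Day 1 in Group 1 it is labelled T1 (0.05 mg) although no CBP-307 has been given. On Day 1 in Group 2A and Day 16 in Group 2B it is labelled T7 although no moxifloxacin has been given. A QTcF above 450 ms, or a T-wave change, seen only on that ECG would be listed as emerging on the drug.

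Categorical outliers and treatment-emergent T-/U-wave changes are secondary endpoints (Section 4.3). At stake are a factual misattribution in the cardiac safety report and a rule that two programmers could implement differently, since one family of outlier tables is limited to post-dose values and the others are not.

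**Working it through.** The plan gives no outlier rate or time-point count, so there is no figure to reproduce. The check has two parts.

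**1. Does the text admit the pre-dose record?**
- Table 2 uses one condition for the by-time point set and for the continuous part of the categorical set.
- Section 6.1 says the time term of the by-time point model includes the pre-dose point. Post-baseline therefore includes pre-dose in that set, and the same words should carry the same meaning in the neighbouring row.
- Table 1 in the same section says post-dose where that is meant (QT/QTc and PK/QTc populations), so the authors had the narrower term available.
- Sections 6.4 and 6.5 do not remove the record afterwards.

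**2. How large is the effect?**

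*Records.* The schedule gives 1 pre-dose + 9 post-dose = 10 per profile. With 34 subjects, T1, T7 and T8 each have 34 × 10 = 340 records against 34 × 9 = 306 post-dose. T4 exists only in Group 2B (Table 3): 17 × 10 = 170 against 17 × 9 = 153. The pre-dose share is 1/10 in each.

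*Time-point rate in one arm.* Let r be the post-dose outlier rate and q the pre-dose rate. The pooled rate is (9r + q)/10, so the relative change against post-dose only is (q/r − 1)/10.

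| q | relative change |
|---|---|
| 0 | −10% |
| 0.5r | −5% |
| r | 0% |
| 2r | +10% |

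Example: r = 5% and q = 0 gives 4.5%.

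*Active minus placebo.* If both arms share the same drug-free q, the difference is [(9rA + q) − (9rP + q)]/10 = 0.9(rA − rP). It is attenuated by 10% whatever q is.

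*Subjects with a T-wave change.* Assume a background rate p per time point, independent time points, and 10 baseline time points that must all be clear. The subject rate is (1 − p)^10 × [1 − (1 − p)^k], with k = 9 (post-dose only) or 10 (pre-dose included).
- p = 1%: 0.904 × 0.0865 = 7.8% against 0.904 × 0.0956 = 8.6%.
- p = 5%: 0.599 × 0.370 = 22.1% against 0.599 × 0.401 = 24.0%.

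*Subjects with new QTcF above 450 ms.* Simulation with no drug effect, new onset judged against the time-matched baseline value:

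| assumed mean; between-/within-subject SD (ms) | 9 points | 10 points |
|---|---|---|
| 405; 14 / 5.7 | 0.54% | 0.57% |
| 410; 15 / 6 | 2.00% | 2.11% |
| 415; 16 / 7 | 6.19% | 6.54% |

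The increase is 0.03 to 0.35 percentage points, or 0.01 to 0.12 of a subject among 34. A single subject with a pre-dose-only event would add 1/34 = 2.9 points to a T1 or T7 incidence.

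**The case against.** **The reading is inferred.** Section 6.1 describes the time term of the models and does not name the categorical or morphological analyses. Other text leans towards post-dose: the QT/QTc population requires a post-dose value, Section 5.5 reports by-time point estimates at post-dose times, and Tables 14.1.9.1 and 14.1.9.2 are limited to post-dose values. This stands in part. The SAP does not say outright that pre-dose ECGs enter these tables, but neither does it exclude them, and its shared wording points to inclusion.

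**Misattribution and dilution pull in opposite directions.** A reader might infer that time-point percentages are diluted by a fixed 10%. The documents do not support that. It needs no pre-dose outliers at all, whereas false attribution needs some. With no drug effect (q = r) the expected rate does not move. Only the between-arm difference shrinks by 10% regardless of q, and only if the arms share q.

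**The comparator carries the same record.** True of T4 and T8, but equal treatment does not cancel the effect, as the 0.9 factor shows.

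**Numerator and denominator for HR, PR and QRS.** A reader might infer that they are mismatched, because the numerator is post-dose and the denominator is all observed time points. Section 6.4 does not say whether pre-dose points are counted for those tables, so a mismatch is possible but not established.

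**Nothing important depends on it.** This stands. T1 is the 0.05 mg titration dose, and assay sensitivity is decided by the moxifloxacin concentration-QTc model (Section 6.2), not by outlier counts.

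**Conclusion.** The point holds as a minor inconsistency. Followed as written, the rules let an ECG recorded before the active drug be tabulated as treatment-emergent for T1 or T7 in the QTcF and T-/U-wave tables, while the HR, PR and QRS tables are limited to post-dose values.

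One record in ten per profile is affected. The single-arm effect on time-point rates is at most a 10% relative reduction and can be nil or positive. Subject counts can only rise, by 0.8 to 1.9 points for T-wave changes (8.6 − 7.8 and 24.0 − 22.1) and by 0.03 to 0.35 points for QTcF above 450 ms. These subject figures rest on assumed background rates, independent time points, and assumed QTcF means and SDs; the SAP gives none of them.

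It would be wrong to extend this to the main results. On Days 6 and 15 the pre-dose ECG follows earlier CBP-307 doses and is genuinely on treatment. The primary criterion and the assay-sensitivity test do not use these counts.

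**What to change.** In Table 2 and Sections 6.4 and 6.5, restrict the categorical and morphological analyses for T1, T4, T7 and T8 to post-dose time points, in both numerator and denominator. Keep the pre-dose point for T2, T3, T5 and T6. Align the descriptions of Tables 14.1.7 to 14.1.10 with this rule. The concentration-QTc and by-time point models stay as they are.

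The cost is a wording change and one record-level flag, with no new data. There are two side effects, and each needs a footnote:
- The four labels will have 9 time points per subject against 10 on Days 6 and 15, so subject-level incidence is not based on the same number of looks across days.
- The Group 2A Day 15 pre-dose ECG serves two labels in Table 3. It will be kept under T6 and dropped under T8.
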